- r PK blood collection will occur just prior to and 2-3 hours after doses on Day 3 and last day of test article. On days of PK collection, the date and time of last food intake prior to dosing will be collected.
- s Starting on Day 2, subjects may be switched to po medication based on clinical stability and investigator discretion.
- t A PTE will occur on Day 21 (± 2 days) for all subjects.
- u The Final Follow-up may be performed via phone call. The visit should be in person if potential recurrence is known, so the procedures to be completed. If they are not known and the subject mentions it during the call, the subject must be asked to come to the clinic as soon as possible for an in person visit where the procedures will be conducted.
- v Height should be collected only at screening.

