# 4.4 Clinically Evaluable Population

The clinically evaluable (CE) population will consist of all ITT subjects who received test article, have acute uncomplicated pyelonephritis (AP), an assessment of outcome, and meet all other evaluability criteria.

Inclusion into the CE populations will be determined programmatically based on the data on the eCRF and a manual review by the Sponsor as necessary prior to unblinding. Details on allocation to each CE population are described in the Pathogen and CE.

Since patient count may differ depending on timepoint, CE populations will be defined by milestone visit (CE-EOT, CE-PTE and CE-FFU). To be included in the populations, subjects must meet all criteria defined below:

1. Qualifying infection:

Inclusion Criterion #2: Females age 18 years or older

93 Version: 1.0 Status: Approved Approved Date: PTK0796-AP-17202 Statistical Analysis Plan

Omadacycline (PTK 0796)

Paratek Pharma, LLC

PTK0796-AP-17202 Statistical Analysis Plan

Inclusion Criterion #3: Clinical signs and symptoms of acute uncomplicated pyelonephritis with onset or worsening within 96 hours prior to randomization.

Inclusion Criterion #4: A clean-catch midstream urine sample with dipstick analysis positive (at least ++) for leukocyte esterase or pyuria (white blood cell [WBC] count >  $10/\mu$ L in unspun urine or  $\ge 10$  per high power field in spun urine sediment).

2. Assessment of Outcome for CE population:

Subjects must meet all of the following to be included in the CE populations:

- Subject did not meet one of the exclusion criteria 6 through 15 of the protocol (Baseline event exclusion)
- Received the randomized test article and was at least 80% compliant with the dosing regimen (Compliance to test article intake).
- Study personnel involved in the assessment of efficacy remained blinded to study treatment, unless a treatment limiting AE occurred which required emergency unblinding. In addition, for each endpoint the following needs to be satisfied, as appropriate:
  - a. For the CE-EOT population:
    - i. Completed the investigator's assessment of clinical response (i.e., was not deemed an indeterminate outcome) at the EOT visit, and
    - ii. The EOT visit occurred on the day of, or within  $\pm 2$  days, following the last dose of test article (3 days window).
  - b. For the CE-PTE population:
    - i. The Overall Clinical Response (based on the investigator's assessment) at the PTE Visit is not Indeterminate (see Table 5).

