    - ii. The PTE Visit occurred Day 21 (± 2 days), unless the subject was considered to be a Clinical Failure based on the investigator's assessment at the EOT visit.
  - c. For the CE-FFU population:
    - i. The overall Clinical Response (based on the investigator's assessment) at the Final Follow-up (FFU) Visit is not Indeterminate.
    - ii. The FFU Visit occurred on Day 28 ( $\pm$  2 days) from the first dose of test article), unless the subject was considered to be a Clinical Failure based on the investigator's assessment at the PTE visit.
- 3. Other Evaluability Criteria
  - a. Prior Antibiotic Therapy

Exclusion Criterion #2: Receipt of any dose of a potentially therapeutic antibacterial agent (with potential activity against uropathogens in the urinary tract) from 72 hours prior to randomization until the first dose of test article. [Note: Subjects who developed the current pyelonephritis while receiving prophylactic antibacterial

93 Version: 1.0 Status: Approved Approved Date: PTK0796-AP-17202 Statistical Analysis Plan

Omadacycline (PTK 0796)

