#### b. Concomitant Antibiotic Therapy

Subjects who receive any systemic concomitant antibiotic therapy from the start of administration of the first dose of test article through the EOT visit (CE-EOT population), PTE visit (CE-PTE population) or FFU visit (CE-FFU population) that is potentially effective against the baseline pathogen, will be excluded from the CE population. If no pathogen is isolated and the systemic concomitant antibiotic is effective against Gram-negative uropathogens, the subject will be excluded from the respective CE population. Subjects who are a clinical failure on the particular visit and received non-study antibiotics for insufficient therapeutic effect of the test article, will not be excluded from the CE populations. Subjects who receive a systemic concomitant antibiotic that is not potentially effective against the baseline pathogen will be included in the CE populations.

c. Evaluable Success and Failure

Evaluable success: The subject received at least 3 doses of active test article and the investigator classifies the subject as a clinical success at the EOT visit (CE EOT population) or the overall clinical response (based on the investigator's assessment) at the PTE visit (CE-PTE population) or the overall clinical response (based on the investigator's assessment) at the FFU visit (CE-FFU population) is clinical success/cure.

Evaluable failure: The subject received at least 2 doses of active test article and the investigator classifies the subject as a clinical failure at the EOT visit (CE EOT population) or the overall clinical response (based on the investigator's assessment) at the PTE Visit (CE-PTE population) or the overall clinical response (based on the investigator's assessment) at the FFU visit (CE-FFU population) is clinical failure/relapse.

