#### 4.5 Microbiologically Evaluable Populations

The microbiologically evaluable (ME) population will include subjects in the CE and micro-ITT populations who have both an appropriately collected post-baseline urine sample and an interpretable post-baseline urine sample. An interpretable post-baseline urine culture is one that has a clearly identified pathogen or one where the baseline pathogen(s) can be excluded (ie, there is no growth of the baseline pathogen).

Since patient count may differ depending on timepoint, ME populations will be defined by milestone visit (ME-EOT and ME-PTE).

93 Version: 1.0 Status: Approved Approved Date: PTK0796-AP-17202 Statistical Analysis Plan

Omadacycline (PTK 0796)

Paratek Pharma, LLC

PTK0796-AP-17202 Statistical Analysis Plan

The ME populations consist of subjects in the micro-ITT population and the CE-EOT and CE-PTE populations, respectively who also have:

- A clean-catch urine specimen at the EOT and PTE visits, and
- Interpretable urine culture results at the EOT and PTE visits.

Subjects with an unfavorable microbiological outcome at EOT will be included in the ME-PTE population, regardless of whether they provide a urine culture at the PTE visit.

An interpretable post-baseline urine culture is one that has a clearly identified pathogen or one where the baseline pathogen(s) can be excluded (i.e., there is no growth of the baseline pathogen). A urine culture is considered uninterpretable if more than two bacterial isolates are identified, unless any of the following is observed:

- There is  $<10^4$  CFU/mL of the baseline pathogen(s), indicating eradication.
- There is  $\geq 10^4$  CFU/mL of the baseline pathogen(s), indicating persistence

At any visit after Screening, a pathogen the same species as the Baseline pathogen with a CFU count of  $\ge 1 \times 10^4$  CFU/mL should be considered a persisting pathogen.

At any visit after Screening, any culture with a CFU count of  $< 10^4$  CFU/mL should be considered a negative culture.

PTK0796-AP-17202 Statistical Analysis Plan

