#### 7.1.1.2 Investigator's Assessment of Clinical Response at PTE

For subjects who were determined to be a clinical success or indeterminate at the EOT visit, the investigator will determine whether or not the subject meets the criteria of 1 of the following clinical outcomes:

- **Clinical Success**: The complete resolution or significant improvement of the baseline signs and symptoms of AP symptoms at the PTE such that no additional antimicrobial therapy is required for the current infection.
- **Clinical Failure**: No apparent response to therapy or persistence of signs and symptoms of infection or reappearance of signs and symptoms at or before the PTE visit such that use of additional systemic antimicrobial therapy for the current infection is required, or death occurred at or before the PTE visit.
- Indeterminate: PTE visit not completed.

Overall Clinical Response at PTE (based on the investigator's assessment) is determined as follows (Table 5) from the investigator's assessments at the EOT and PTE Visits:

EOT Visit	PTE Visit	Overall Clinical Response at PTE Visit
Success	Success	Success
Success	Failure	Failure
Success	Indeterminate	Indeterminate
Failure	Success	Failure
Failure	Failure	Failure
Failure	Indeterminate	Failure
Indeterminate	Success	Indeterminate
Indeterminate	Failure	Failure
Indeterminate	Indeterminate	Indeterminate

 Table 5
 Investigator's Assessment of Clinical Response at PTE Visit

EOT = end of treatment; PTE = post-therapy evaluation.

The derived Overall Investigator's Clinical Response is based on the "worst case scenario" to accommodate for missing visit assessment and intercurrent events (eg rescue medication at EOT visit). For the ITT and micro-ITT populations, the proportion of subjects with a Clinical Success is defined using the following formula (missing information at the PTE visit will be counted as Indeterminate):

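### The CE-PTE window rule exempts only end-of-treatment failures, so an established later failure with no Day 19-23 visit drops out of CE-PTE and ME-PTE

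*SAP*

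**What the plan says.** The conditions in SAP 4.4 are cumulative: "To be included in the populations, subjects must meet all criteria defined below". CE-PTE has two visit-specific conditions. Item b.i requires an overall clinical response at PTE that is not indeterminate. Item b.ii requires the PTE visit on Day 21 ± 2, "unless the subject was considered to be a Clinical Failure based on the investigator's assessment at the EOT visit".

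Other parts of the plan bear on the same subject:

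- SAP 7.1.1.2 counts as clinical failure at PTE any "reappearance of signs and symptoms at or before the PTE visit such that use of additional systemic antimicrobial therapy for the current infection is required", and also death at or before that visit. Table 5 turns EOT success followed by PTE failure into overall failure.
- SAP 4.4 item 3b says that subjects who are failures at the visit in question and "received non-study antibiotics for insufficient therapeutic effect of the test article, will not be excluded from the CE populations".
- SAP 4.5 builds ME on CE: "The ME populations consist of subjects in the micro-ITT population and the CE-EOT and CE-PTE populations, respectively who also have" usable urine cultures. Its carry-forward into ME-PTE covers only an unfavourable microbiological outcome at EOT.
- SAP 4.4 item c.ii repeats the construction for CE-FFU, exempting only clinical failure at PTE.
- SAP 5.4 uses EOT, PTE and FFU data in ITT and micro-ITT whenever they were collected.
- Protocol Appendix 1 fixes the visit: "A PTE will occur on Day 21 (± 2 days) for all subjects".

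**The concern.** A visit window is a fair condition for a success, because success means having been watched long enough. It adds nothing for a subject who has already failed, since a visit on Day 17 or Day 25 does not change that outcome. Elsewhere the SAP follows this principle: it keeps rescued failures in CE and EOT microbiological failures in ME-PTE. Item b.ii departs from it for every failure arising after EOT, and for a rescued relapse it gives the opposite answer to item 3b. CE membership is to be derived by program, so the conflict has to be settled in the text.

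SAP 7.2.1 also provides the difference in success rates, its credible interval and the posterior probability of non-inferiority for CE and ME. These analyses are read as a check on ITT. If they lose post-EOT failures unevenly between arms, they could understate a durability problem in one regimen.

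**Working it through.** **Four subjects taken through the rules**, all clinical successes at EOT:

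- Relapse and rescue on Day 15, PTE visit on Day 21: overall failure, in window, kept.
- Same relapse, PTE visit on Day 17 or Day 25: overall failure in Table 5. Item b.i is met and b.ii is not. Item 3b says not excluded, but all criteria must hold, so the literal result is exclusion from CE-PTE and ME-PTE. The ME carry-forward does not help unless the EOT culture was already unfavourable.
- Death on Day 16: a defined failure for which no in-window visit can occur. Lost by construction.
- No relapse, PTE visit on Day 17 or Day 25: a success, also excluded.

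**Formula.** Let S be the true success proportion, E the failures called at EOT and L the failures first arising after EOT, with S + E + L = 1. Let w and v be the shares of successes and of late failures that are out of window. Then

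CE-PTE success = S(1-w) / [S(1-w) + E + L(1-v)].

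This exceeds S only if (1-w)(E+L) > E + L(1-v), that is, v/w > (E+L)/L. The threshold is 4.0, 2.0, 1.33 or 1.0 when 25%, 50%, 75% or 100% of failures arise after EOT.

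The plan states no figure for window losses. All values of w, v and L below are assumptions.

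**One arm, S = 0.80**

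| Late failures L | w = 0, v = 50% | w = v = 10% |
|---|---|---|
| 5% | 0.80/0.975 = 82.1% | 0.72/(0.72+0.15+0.045) = 78.7% |
| 10% | 0.80/0.95 = 84.2% | 0.72/(0.72+0.10+0.09) = 79.1% |

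The rate rises above 80% in the first column and falls below it in the second.

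**Two arms, true 75% v 80% (difference -5.0), L = 10% v 4%, so E = 15% v 16%**

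| w | v | CE-PTE rates | Difference |
|---|---|---|---|
| 0 | 50% | 0.75/0.95 = 78.9% v 0.80/0.98 = 81.6% | -2.7 |
| 5% | 50% | 0.7125/0.9125 = 78.1% v 0.76/0.94 = 80.9% | -2.8 |
| 10% | 50% | 0.675/0.875 = 77.1% v 0.72/0.90 = 80.0% | -2.9 |
| 10% | 10% | 0.675/0.915 = 73.8% v 0.72/0.916 = 78.6% | -4.8 |

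**At the planning rates.** SAP 3.1 uses 0.69 and 0.78. These are composite rates, used here only for scale. With half of failures late, w = v = 10% gives 0.678 and 0.771; w = 5% with v = 50% gives 0.738 and 0.818. If true rates are equal but 75% of failures are late in one arm and 25% in the other (w = 5%, v = 50%), an apparent gap of 6.5 points (0.772 v 0.707) or 5.0 points (0.843 v 0.794) arises.

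**The case against.** A reader might infer that the rule removes failures selectively and so tilts CE-PTE towards non-inferiority. The documents do not support that. The same sentence drops out-of-window successes and always keeps EOT failures. With equal out-of-window shares it lowers the success rate or leaves it unchanged. A figure such as 82.1% or 84.2% for a true 80% requires that no success is ever seen out of window.

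Nor do the documents describe a mechanism that pushes relapsing subjects out of window. PTE is set for the same days in everyone. Failure includes "reappearance of signs and symptoms at or before the PTE visit", so an earlier relapse can be recorded at an in-window visit and the subject kept. Relapsing subjects may well be seen early, but that is conjecture.

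Item 3b can also be read as already keeping the rescued relapse. SAP 4.4 provides for manual review before unblinding and refers details to the Pathogen and CE Review Plan, which is not among these documents. Finally, the numbers are small: with about 200/5 = 40 randomised per arm, 5% late failures with half out of window is one subject per arm, and 10% is two.

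All of this stands against a claim of demonstrated bias. It does not remove the conflict between b.ii and item 3b, and it does not reach deaths after EOT and before Day 19, which no reading of item 3b restores.

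**Conclusion.** The gap in the text is real. Under b.ii as written, a subject who is an established failure after EOT but has no PTE visit on Day 19-23 is excluded from CE-PTE and ME-PTE, against the failure definition in SAP 7.1.1.2 and, for rescued subjects, against item 3b.

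Its effect is conditional. Inflation needs v/w > (E+L)/L, and the documents give none of these quantities. In the two-arm example the apparent difference runs from nearly unbiased (-4.8) to roughly half the true one (-2.7 to -2.9), depending on how much more often late failures than successes miss the window.

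The reach is limited to CE and ME analyses in a study whose SAP calls all efficacy endpoints exploratory. ITT and micro-ITT are unaffected. This is an inexpensive correction to make before unblinding; it does not undermine the main results.

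**What to change.** 1. Reword b.ii to exempt any subject who met clinical failure, including death, at EOT or at any time after EOT up to the end of the PTE window.
2. Align item 3b and the ME-PTE carry-forward in SAP 4.5 with that wording, so that all three give one answer.
3. For CE-FFU, exempt relapse or death after PTE in c.ii. Also reconcile the sentence in SAP 7.1.1.3 that makes the response indeterminate when the FFU assessment is out of window (it names the EOT response, apparently a slip). If it is meant for FFU, c.i would still exclude the subject and changing c.ii alone would achieve nothing.
4. Tabulate window exclusions by outcome and arm, and add a sensitivity analysis of CE-PTE and ME-PTE that ignores the window.

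The cost is a few phrases, one table and one repeat analysis. The downside is that out-of-window successes are still dropped while failures are kept, so the CE rate may read slightly low. With v = 0 and w = 5%, a true 0.69 reads 0.6555/(0.6555+0.31) = 0.679 and a true 0.78 reads 0.741/(0.741+0.22) = 0.771. The sensitivity analysis would show how much this matters.

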#### PTK0796-AP-17202 Statistical Analysis Plan

therapy (for any reason) may be eligible if all prophylactic antibacterials are stopped (no further dosing after randomization) and approved by the study medical monitor.] Subjects who meet exclusion criteria #5 will be excluded from the CE populations.

#### b. Concomitant Antibiotic Therapy

Subjects who receive any systemic concomitant antibiotic therapy from the start of administration of the first dose of test article through the EOT visit (CE-EOT population), PTE visit (CE-PTE population) or FFU visit (CE-FFU population) that is potentially effective against the baseline pathogen, will be excluded from the CE population. If no pathogen is isolated and the systemic concomitant antibiotic is effective against Gram-negative uropathogens, the subject will be excluded from the respective CE population. Subjects who are a clinical failure on the particular visit and received non-study antibiotics for insufficient therapeutic effect of the test article, will not be excluded from the CE populations. Subjects who receive a systemic concomitant antibiotic that is not potentially effective against the baseline pathogen will be included in the CE populations.

c. Evaluable Success and Failure

Evaluable success: The subject received at least 3 doses of active test article and the investigator classifies the subject as a clinical success at the EOT visit (CE EOT population) or the overall clinical response (based on the investigator's assessment) at the PTE visit (CE-PTE population) or the overall clinical response (based on the investigator's assessment) at the FFU visit (CE-FFU population) is clinical success/cure.

Evaluable failure: The subject received at least 2 doses of active test article and the investigator classifies the subject as a clinical failure at the EOT visit (CE EOT population) or the overall clinical response (based on the investigator's assessment) at the PTE Visit (CE-PTE population) or the overall clinical response (based on the investigator's assessment) at the FFU visit (CE-FFU population) is clinical failure/relapse.

#### 4.5 Microbiologically Evaluable Populations

The microbiologically evaluable (ME) population will include subjects in the CE and micro-ITT populations who have both an appropriately collected post-baseline urine sample and an interpretable post-baseline urine sample. An interpretable post-baseline urine culture is one that has a clearly identified pathogen or one where the baseline pathogen(s) can be excluded (ie, there is no growth of the baseline pathogen).

Since patient count may differ depending on timepoint, ME populations will be defined by milestone visit (ME-EOT and ME-PTE).

93 Version: 1.0 Status: Approved Approved Date: PTK0796-AP-17202 Statistical Analysis Plan

Omadacycline (PTK 0796)

Paratek Pharma, LLC

PTK0796-AP-17202 Statistical Analysis Plan

The ME populations consist of subjects in the micro-ITT population and the CE-EOT and CE-PTE populations, respectively who also have:

- A clean-catch urine specimen at the EOT and PTE visits, and
- Interpretable urine culture results at the EOT and PTE visits.

Subjects with an unfavorable microbiological outcome at EOT will be included in the ME-PTE population, regardless of whether they provide a urine culture at the PTE visit.

An interpretable post-baseline urine culture is one that has a clearly identified pathogen or one where the baseline pathogen(s) can be excluded (i.e., there is no growth of the baseline pathogen). A urine culture is considered uninterpretable if more than two bacterial isolates are identified, unless any of the following is observed:

- There is  $<10^4$  CFU/mL of the baseline pathogen(s), indicating eradication.
- There is  $\geq 10^4$  CFU/mL of the baseline pathogen(s), indicating persistence

At any visit after Screening, a pathogen the same species as the Baseline pathogen with a CFU count of  $\ge 1 \times 10^4$  CFU/mL should be considered a persisting pathogen.

At any visit after Screening, any culture with a CFU count of  $< 10^4$  CFU/mL should be considered a negative culture.

PTK0796-AP-17202 Statistical Analysis Plan

# **5 OVERALL STATISTICAL CONSIDERATIONS**

## 5.1 General

All analyses will use SAS version 9.4 or higher. Results will be reported by treatment group, unless otherwise specified.

Unless otherwise stated, listings corresponding to all summaries will be provided. Generally, listings will be provided for all randomized patients, however sometimes they may be limited to a smaller set depending on parameter (e.g. compliance to a test article will be limited to safety population).

Unless otherwise noted, categorical variables will be summarized using counts and percentages. Percentages will be rounded to one decimal place, except 100% will be displayed without any decimal places and percentages will not be displayed for zero counts.

Continuous variables will be summarized using the number of observations (n), mean, standard deviation (SD), median, minimum and maximum.

## 5.2 Definitions

In Table 2 general definitions are provided used in the statistical analysis.

Variable	Definition		
Baseline	Unless otherwise stated, baseline is defined as the value closest to but prior to the initiation of test article administration.		
Change from baseline	Change from baseline will be defined as the post-baseline value minus the baseline value (on a subject level). Change from baseline will only be calculated for subjects who have both baseline and at least one post-baseline value for any parameter.		
Duration Variables	Duration variables will be calculated using the general formula:		
	Duration (days) = End date - Start date + 1		
	If applicable, where time is collected:		
	Duration (hh:mm) = End datetime - Start datetime		
Calculated Creatinine Clearance (mL /min),	(140 – age [yrs]) * weight [kg] * Z	Z = 0.85 for Female subjects	
Cockcroft-Gault equation	Creatinine [mg/dL] * 72		
Body Mass Index (BMI)	$BMI = Weight (kg) / Height (m)^2$		

